⁵ CK-MB (preferred), or Troponin (cTn) if CK-MB is not available, are drawn within 24 hours prior to the start of the PCI procedure. Blood can be withdrawn from the arterial sheath prior to the index procedure.

For patients showing elevated Troponin (e.g. non-STEMI patients) at baseline (within 24h pre-PCI) an additional blood sample must be collected prior to the PCI procedure to confirm that:

- hs-cTn or Troponin I or T levels are stable, i.e. the value should be within 20% range of the value found in the first sample at baseline, or have dropped
- CK-MB and CK levels are within normal range

If hs-cTn or Troponin I or T levels are stable or have dropped, the CK-MB and CK levels are within normal ranges, and the ECG is normal, the patient may be included in the study.

⁶ CK-MB (preferred), or Troponin (cTn) if CK-MB is not available, are determined within 10-14 hours and 22-26 hours post-procedure or at discharge if sooner. If cardiac enzymes are elevated (CK >2ULN with iso-enzyme CKMB, CKMB >3 ULN, or cTn/hs-cTn >35 ULN), serial measurements of cardiac enzymes must be taken until a decline is noted.

⁷ iFR pre-procedure is mandatory to explore the physiological importance of the left main bifurcation disease.

ⁱⁱ IVUS assessment post-stent implantation for optimization of BiOSS LIM C deployment is highly recommended according to ESC guidelines (Class IIa, level of evidence: B)

⁷ Collect and forward to central Core Lab (material collection only).

⁸ For all intercurrent angiographies and revascularizations (incl. stent thrombosis, etc.), the angiogram must be sent to the Monitor organization and/or CRO (Cardialysis).

⁹ It is recommended to attempt achieving a residual SYNTAX Score ≤8 post PCI. A SYNTAX Score assessment post-PCI is optional for the investigators.

Note: In the event of intercurrent illnesses, interventions, adverse events, or treatment failure, effort should be made to complete the required observations as much as possible.

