3 OBJECTIVE

To establish the safety and efficacy of the BiOSS LIM C with respect to Patient oriented Composite Endpoint (PoCE) at 12 months in a “real world” left-main bifurcation population and compared with a pre-specified performance goal.

**Since the sample size and power calculation of the POLBOS LM study is based on the outcome of the EXCEL trial as an objective performance goal, the in- and exclusion criteria, general recommendations for practice, treatment and (endpoint) definitions are similar to the EXCEL protocol as published in NEJM and referred as such.³*

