5 ENDPOINTS

5.1 Primary Endpoint

The primary endpoint for this trial is defined as the patient-oriented composite endpoint (PoCE) at 12 months post-procedure. PoCE is a composite measure of

- All-cause mortality
- Stroke (modified Rankin Scale (mRS≥1)
- Any Myocardial Infarction* (includes nontarget vessel territory)
- Any unplanned revascularization for ischemia (includes all target and nontarget vessels)

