7.8 Hospital Discharge (post-PCI to hospital discharge)

At discharge, from the hospital where the index procedure took place, an assessment of angina status and cardiovascular drug use will be performed. Any Serious Adverse Events will be recorded and an ECG will be performed. The patient must be informed of the required DAPT medication and follow-up visits per protocol should be scheduled prior to discharge.

In addition, CK-MB (preferred) or Troponin (cTn) if CK-MB is not available, in the post-procedure hospitalization period should be taken at 12 hrs (± 2 hrs; i.e. 10-14 hrs) and 24h (± 2 hrs; i.e. 22-26 hrs) post procedure or at discharge if sooner.

If cardiac enzymes are elevated (CKMB >3 ULN, or cTn/hs-cTn >35 ULN), serial measurements of cardiac enzymes must be taken until a decline is noted. In any case of cardiac enzyme elevation (CK >2ULN with iso-enzyme CKMB, CKMB >3 ULN, or cTn/hs-cTn >35 ULN) at least two samples (with an preferred interval of 6 hours) should be obtained prior to discharge.

Additional serial troponins or CK-MBs should be drawn at any time in case of any adverse cardiac event.

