8.1 Primary Analysis

The primary analysis is an analysis of the primary endpoint, being PoCE at 12-months. The study is powered at 80% to show non-inferiority for the BiOSS LIM C when compared to XIENCE. The BiOSS LIM C suspected PoCE assumption is based on the assumption of no difference in event rates between BiOSS LIM C and XIENCE.

The 95% one-sided confidence interval will be calculated for the PoCE rate at 12 months, using Kaplan-Meier estimates at 12 months and its standard deviation; the KM-estimate is assumed to be normally distributed.

The upper limit of the interval will be compared with a performance target, being the reported PoCE in the EXCEL trial plus a non-inferiority margin. If the 95% interval excludes the performance target, BiOSS LIM C will be considered to be non-inferior to XIENCE (this accounts to an one-sided non-inferiority testing with a significance level (alpha of 5%).

Statistical analyses will be performed with either SAS software system (SAS Institute Inc., Cary, North Carolina) version 9.3 or higher.

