Platelet transfusions should be recorded and reported but are not included in these definitions until further information is obtained about the relationship to outcomes.

If a CABG-related bleed is not adjudicated as at least a type 3 severity event, it will be classified as not a bleeding event. If a bleeding event occurs with a clear temporal relationship to CABG (i.e., within a 48-h time frame) but does not meet type 4 severity criteria, it will be classified as not a bleeding event.

*Corrected for transfusion (1 U packed red blood cells or 1 U whole blood = 1 g/dL hemoglobin).

†Cell saver products are not counted.

CABG indicates coronary artery bypass graft

DEATH

(ARC)⁴²

The deaths will be adjudicated per the ARC definition: All deaths are considered cardiac unless an unequivocal non-cardiac cause can be established. Specifically, any unexpected death even in patients with coexisting potentially fatal non-cardiac disease (e.g. cancer, infection) should be classified as cardiac.

- **Cardiac death:**

Any death due to proximate cardiac cause (e.g. MI, low-output failure, fatal arrhythmia), unwitnessed death and death of unknown cause, all study procedure related deaths including those related to concomitant treatment.

- **Vascular death:**

Death due to non-coronary vascular causes such as cerebrovascular disease, pulmonary embolism, ruptured aortic aneurysm, dissecting aneurysm, or other vascular cause.

- **Non-cardiovascular death:**

Any death not covered by the above definitions such as death caused by infection, malignancy, sepsis, pulmonary causes, accident, suicide or trauma.

MYOCARDIAL INFARCTION (MI)

EXCEL study definition

Peri/Post procedure MI:

Defined as the occurrence within 72 hours after PCI of either:

- CK-MB $\geq 10x$ ULN or cTn* (I or T) $\geq 70x$ ULN,
- OR: CK-MB $\geq 5x$ ULN or cTn* (I or T) $\geq 35x$ ULN in combination with any of the following:
 - new pathological Q waves in at least 2 contiguous leads or new persistent non-rate related LBBB, or
 - angiographically documented native coronary artery occlusion or new severe stenosis with thrombosis and/or diminished epicardial flow, or
 - imaging evidence of new loss of viable myocardium or new regional wall motion abnormality

*while EXCEL definition did not comprise cTn, we consider equivalence CK-MB $\geq 10x$ versus cTn $\geq 70x$ and CK-MB $\geq 5x$ versus cTn $\geq 35x$ ⁴³

Spontaneous MI*

Defined as the occurrence >72 hours after any PCI of:

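### Peri-procedural MI in the primary endpoint is not measured as in the EXCEL benchmark: Appendix I accepts CK-MB or troponin with no order of precedence

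*Combined protocol and SAP*

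**What the plan says.** - **Adjudication rule.** Appendix I, under a heading that attributes the definition to EXCEL, has two routes to peri-procedural MI within 72 hours after PCI. The biomarker-only route is "CK-MB $\geq 10x$ ULN or cTn* (I or T) $\geq 70x$ ULN". The second route is "OR: CK-MB $\geq 5x$ ULN or cTn* (I or T) $\geq 35x$ ULN in combination with any of the following", where the supporting evidence is ECG, angiographic or imaging. In both routes the two markers are joined by a plain or.
- **Departure from EXCEL.** The footnote to these cut-offs reads "while EXCEL definition did not comprise cTn, we consider equivalence" and cites a consensus definition for the pairing of 10x with 70x and 5x with 35x.
- **Sampling.** Note 6 to the schedule in section 1.1 says "CK-MB (preferred), or Troponin (cTn) if CK-MB is not available, are determined within 10-14 hours and 22-26 hours post-procedure". Section 7.8 repeats the order: "CK-MB (preferred) or Troponin (cTn) if CK-MB is not available, in the post-procedure hospitalization period".
- **Comparability claim.** Section 3 says that "the in- and exclusion criteria, general recommendations for practice, treatment and (endpoint) definitions are similar to the EXCEL protocol". Section 8.5 chooses day 0 so that the rate is comparable with the EXCEL-derived goal.
- **Decision rule.** Section 8.1: "The upper limit of the interval will be compared with a performance target, being the reported PoCE in the EXCEL trial plus a non-inferiority margin". Section 8.2 gives 16.7% and 6.3%.
- **What is absent.** Section 8 plans no analysis by marker. Section 8.6 plans no sensitivity analysis for missing data other than Kaplan-Meier censoring.

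**The concern.** In a single-arm trial against a fixed number, nothing inside the study cancels a difference in measurement. If a component of PoCE is ascertained differently from the component inside the 16.7%, the observed rate moves for reasons unrelated to the stent, while the 23.0% target stays put.

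The sampling sections treat troponin as a stand-in for CK-MB, but the rule that the Clinical Event Committee applies does not carry that order over. Two situations follow:

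- **Both markers available after PCI.** A patient can qualify on troponin although CK-MB does not qualify. The or can only add MIs relative to a CK-MB-only rule.
- **Only troponin available.** One marker replaces the other. Whether 70x and 35x capture more, as many or fewer MIs than 10x and 5x CK-MB is assumed and not checked.

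Added MIs make non-inferiority harder to show. Missed MIs make it easier to show for a device that does not deserve it.

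The point concerns peri-procedural MI only. The spontaneous MI definition also accepts either marker, and the protocol notes no difference from EXCEL there.

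**Working it through.** **Step 1: the plan's own sample size.** Inputs from section 8.2: expected rate p1 = 0.167, target p0 = 0.167 + 0.063 = 0.230, one-sided alpha 5%, power 80%.

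n = [1.645·√(0.23·0.77) + 0.842·√(0.167·0.833)]² / 0.063² = 255.04, rounded up to 256. The stated figure reproduces, and this point does not alter it.

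**Step 2: pass limit under the planned analysis.** Section 8.1 compares a normal-theory upper limit with 23.0%. I assume complete follow-up, so the Kaplan-Meier estimate is the simple proportion x/256.

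- x = 48: 0.1875 + 1.645·√(0.1875·0.8125/256) = 0.1875 + 0.0401 = 0.2276, pass.
- x = 49: 0.1914 + 1.645·√(0.1914·0.8086/256) = 0.1914 + 0.0404 = 0.2318, fail.

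The trial passes with 48 events or fewer. Binomial probabilities of that are 83.3% at a true rate of 16.7% and 5.9% at 23.0%. The exact test used for sizing passes at 47 or fewer, with 78.9% and 4.3%.

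**Step 3: which patients depend on the marker.** Suppose both markers were measured after PCI.

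| CK-MB | Troponin | Supporting evidence | MI on CK-MB alone | MI under Appendix I |
|---|---|---|---|---|
| ≥10x | any | any | yes | yes |
| 5x to <10x | any | present | yes | yes |
| 5x to <10x | ≥70x | absent | no | yes |
| <5x | ≥70x | any | no | yes |
| <5x | 35x to <70x | present | no | yes |

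Only the last three rows differ, and they change PoCE only in patients with no other primary event by 12 months.

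**Step 4: effect of a net shift.** The documents give neither an MI rate nor a discordance rate, so the shifts below are assumptions. One point is 2.56 of 256 patients. Each entry is P(X ≤ 48) with n = 256 at the shifted rate.

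| Assumed shift in measured PoCE | Power, like-for-like rate 16.7% | False-pass probability, like-for-like rate 23.0% |
|---|---|---|
| −2 points | 96.9% | 21.1% |
| −1 point | 92.1% | 11.8% |
| 0 | 83.3% | 5.9% |
| +1 point | 70.4% | 2.7% |
| +2 points | 54.7% | 1.1% |

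The exact rule behaves in the same way: −1 point takes the false-pass probability from 4.3% to 9.0%, and +1 point takes power from 78.9% to 64.6%.

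**The case against.** The best defence has four parts.

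1. **The plan substitutes and does not double-test.** CK-MB is drawn if available, so the or seldom has two values to choose from. The troponin in inclusion criterion 5 is drawn before PCI and puts no second marker into the 72-hour window. This largely stands: dual measurement after PCI is possible, but its frequency is unknown. It is not excluded, because section 7.8 also asks for additional serial troponins or CK-MBs after any adverse cardiac event. The argument also leaves the troponin-only patients, in whom the direction is open.
2. **The departure is disclosed and referenced, and section 3 claims similarity, not identity.** True. The troponin multiples are seven times the CK-MB multiples, and a 260-patient single-arm study cannot be expected to validate a biomarker equivalence. Disclosure does not make the rates like for like, but it does mean that the remedy is to report and bound the difference, not to test the equivalence.
3. **Precedence may be set in the CEC charter.** Section 11.3 says the charter will contain the classification algorithm. The charter is not among the documents, so this may be so. Section 11.3 also ties classification to the protocol definitions, so Appendix I is the place where the rule should be unambiguous.
4. **The size is hypothetical.** It is. The table shows sensitivity to a shift and does not estimate one.

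**Conclusion.** The protocol's own footnote establishes that peri-procedural MI is not measured identically to the benchmark, and Appendix I does not carry over the CK-MB-first order of sections 1.1 and 7.8. What follows is unverified comparability of unknown net direction.

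A reader might infer that the study counts MI more inclusively than EXCEL did. The documents do not support that as a general statement. It holds only where both markers exist after PCI; some patients with CK-MB between 5x and 10x qualify on CK-MB anyway; and where troponin replaces CK-MB, the count could rise, stay the same or fall. A reader might also infer that the or threatens a false claim of non-inferiority. Extra MIs do the opposite: they cost power. The false-positive risk comes only from MIs that troponin misses.

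The stakes are a matter of a few patients: a net shift of one point, about 2.6 of 256, costs some 13 points of power in one direction and doubles the false-pass probability in the other. These figures rest on assumed shifts, complete follow-up and the planned normal limit. The point merits a change because the change is cheap, not because a bias of known size has been shown.

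**What to change.** **Appendix I and the CEC charter.** For the primary endpoint, adjudicate peri-procedural MI on CK-MB whenever a post-procedure CK-MB value exists. Apply the 70x and 35x troponin cut-offs only when none exists.

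**Section 8.1.** Report the number of patients adjudicated on each marker and the number of primary events that rest on troponin alone. Pre-specify a sensitivity analysis of 12-month PoCE limited to patients with a post-procedure CK-MB value. It should not instead count only CK-MB-defined MIs in everyone: that would set peri-procedural MI to zero in troponin-only patients, lower the rate and favour the device. List patients with neither marker, and their events, separately, so that very early deaths do not drop out of the restricted set unnoticed.

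**Cost.** Some wording and one or two tabulations, from samples already planned. Some troponin-positive cases with low CK-MB leave the primary count; report them as a secondary MI category. The restricted analysis has fewer patients and a wider interval, so it is supportive only. The hierarchy does not remove the uncertainty in troponin-only patients; the count by marker shows how large that group is.

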- a rise and/or fall of cardiac biomarkers (CK-MB or troponin) >1x ULN combined with:
 - ECG changes indicative of new ischemia [ST-segment elevation or depression, in the absence of other causes of ST-segment changes such as left ventricular hypertrophy (LVH) or bundle branch block (BBB)], or
 - Development of pathological Q waves (≥ 0.04 seconds in duration and ≥ 1 mm in depth) in ≥ 2 contiguous precordial leads or ≥ 2 adjacent limb leads) of the ECG, or
 - Angiographically documented graft or native coronary artery occlusion or new severe stenosis with thrombosis and/or diminished epicardial flow, or
 - Imaging evidence of new loss of viable myocardium or new regional wall motion abnormality

Each MI will also be adjudicated as:

- ST-segment elevation MI (STEMI)
- Non-ST-segment elevation MI (NSTEMI)
- Each STEMI and NSTEMI will be subcategorized as
 - Q-wave
 - Non-Q-wave
 - Unknown (no ECG or ECG not interpretable)

Target Vessel Myocardial Infarction

Myocardial Infarction not clearly attributable to a non-target vessel.

Non-target Vessel Myocardial Infarction

Myocardial Infarction clearly attributable to a non-target vessel.

◊ for poolability and/or comparison with other studies we may also adjudicate spontaneous MI according to Third Universal definition.

Myocardial infarction according to Third Universal definition (2012)⁴⁴	
MI type 1: Spontaneous MI	
Spontaneous myocardial infarction related to atherosclerotic plaque rupture, ulceration, fissuring, erosion, or dissection with resulting intraluminal thrombus in one or more of the coronary arteries leading to decreased myocardial blood flow or distal platelet emboli with ensuing myocyte necrosis. The patient may have underlying severe CAD but on occasion non-obstructive or no CAD. Needed criteria:	

 ○ Detection of rise and/or fall of cardiac biomarkers (preferably troponin) with at least one value above the 99th percentile of the upper reference limit (URL) together with evidence of myocardial ischaemia with at least one of the following: 	

- Symptoms of ischaemia
- New or presumed new significant ST-segment-T wave (ST-T) changes
- New LBBB
- Development of pathological Q waves in the ECG
- Imaging evidence of new loss of viable myocardium or new regional wall motion abnormality
- Identification of an intracoronary thrombus by angiography or autopsy

MI type 2: MI secondary to an ischaemic imbalance

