In instances of myocardial injury with necrosis where a condition other than CAD contributes to an imbalance between myocardial oxygen supply and/or demand, e.g. coronary endothelial dysfunction, coronary artery spasm, coronary embolism, tachy-/brady-arrhythmias, anemia, respiratory failure, hypotension, and hypertension with or without LVH.

MI type 3: MI resulting in death when biomarker values are unavailable

Cardiac death with symptoms suggestive of myocardial ischemia and presumed new ischemic ECG changes or new LBBB, but death occurring before blood samples could be obtained, before cardiac biomarker could rise, or in rare cases cardiac biomarkers were not collected.

MI type 4a: MI related to PCI (<48 hours post PCI)

Adjudicated per EXCEL/SCAI definition only, see above.

MI type 4b: MI related to stent thrombosis

Myocardial infarction associated with stent thrombosis is detected by coronary angiography or autopsy in the setting of myocardial ischemia and with a rise and/or fall of cardiac biomarkers values with at least one value above the 99th percentile URL.

MI type 4c: MI related to restenosis

Myocardial infarction in the presence of restenosis defined as $\geq 50\%$ stenosis at coronary angiography or a complex lesion associated with a rise and/or fall of cTn values $> 99\text{th}$ percentile URL and no other significant obstructive CAD of greater severity following:

- Initially successful stent deployment ($< 30\%$ stenosis), OR
- Initially successful dilatation of a coronary stenosis with balloon angioplasty ($< 50\%$)

MI type 5: MI related to CABG (<48 hours post CABG)

Adjudicated per EXCEL definition only, see below.

PERI-PROCEDURAL MYOCARDIAL INFARCTION (SCAI 2013)⁴³

Peri-procedural MI according to SCAI 2013 definition

Peri-procedural MI after PCI or CABG (<48 hours post- PCI or CABG)

For patients with normal baseline cardiac biomarkers: any of the following criteria:

- CK-MB $\geq 10 \times \text{ULN}$ or cTn (I or T) $\geq 70 \times \text{ULN}$
- OR: CK-MB $\geq 5 \times \text{ULN}$ or cTn (I or T) $\geq 35 \times \text{ULN}$ in combination with any of the following:
 - New pathologic Q-waves in ≥ 2 contiguous leads
 - OR: new persistent LBBB

For patients with elevated baseline cardiac biomarkers: any of the following criteria:

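### Appendix I has no working rule for MI after CABG: the EXCEL-based classes are timed from PCI only, and the type 5 entry points to EXCEL text that is not there

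*Combined protocol and SAP*

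**What the plan says.** Sections 5.1 and 5.2 and the synopsis tie MI, by footnote, to the EXCEL study definition in Appendix I. Section 11.3 has the Clinical Event Committee (CEC) classify MI by the protocol's definitions.

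The EXCEL block in Appendix I has two classes:

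- Peri/post-procedure MI. The timing phrase is "Defined as the occurrence within 72 hours after PCI of either". The thresholds that it introduces are a CK-MB of at least 10x ULN (troponin 70x), or at least 5x (troponin 35x) with a supporting ECG, angiographic or imaging finding.
- Spontaneous MI. The timing phrase is "Defined as the occurrence >72 hours after any PCI of". The biomarker criterion is then given as "a rise and/or fall of cardiac biomarkers (CK-MB or troponin) >1x ULN combined with", and one of four supporting findings must also be present (ischemic ECG change, pathological Q waves, angiographic occlusion or new severe stenosis, imaging evidence of new loss).

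A Third Universal table follows, introduced as optional: "for poolability and/or comparison with other studies we may also adjudicate spontaneous MI according to Third Universal definition". Its entry "MI type 5: MI related to CABG (<48 hours post CABG" carries the instruction "Adjudicated per EXCEL definition only, see below". The next block is headed "Peri-procedural MI according to SCAI 2013 definition" and covers "Peri-procedural MI after PCI or CABG (<48 hours post- PCI or CABG".

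**The concern.** The type 5 pointer fails twice. The EXCEL text stands above it, not below, and that text contains no criteria for CABG. The operative block has the same gap: only a PCI starts its 72-hour clock, so nothing keeps the peri-operative period out of the spontaneous class.

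The plan foresees CABG during follow-up. Section 7.10 permits repeat CABG with evidence of ischemia, section 9.5 lists urgent CABG as a known risk, and the TLR and TVR definitions include bypass surgery. The spontaneous class even names graft occlusion. Because prior CABG is excluded (section 6.2), a graft can only come from surgery after enrollment.

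At stake is whether the committee scores these events consistently, and whether findings produced by surgery enter the MI and device-oriented endpoints as spontaneous events.

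**Working it through.** No figure in the plan is in dispute here; the sample size and performance target do not depend on this point. The check sets the definitions side by side.

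**1. Coverage**

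| Text in Appendix I | Procedure named | Window | CK-MB threshold |
|---|---|---|---|
| EXCEL peri/post-procedure | PCI | within 72 h | 10x, or 5x plus ECG, angiographic or imaging support |
| EXCEL spontaneous | any PCI | after 72 h | >1x plus one of four supporting findings |
| Type 5 entry | CABG | under 48 h | none given; refers to EXCEL |
| SCAI 2013 | PCI or CABG | under 48 h | 10x, or 5x plus new Q waves or LBBB |

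**2. What each text gives for an event after CABG, more than 72 h after PCI**

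Baseline biomarkers are taken as normal. The middle column asks what the EXCEL peri-procedural criteria would give if they were extended to CABG; the protocol does not say that they are.

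| Finding | EXCEL spontaneous (literal reading) | EXCEL peri-procedural, if extended | SCAI (event under 48 h) |
|---|---|---|---|
| CK-MB <10x, no supporting finding | no | no | no |
| CK-MB >1x and <5x, new wall motion abnormality | MI | no | no |
| CK-MB 5x to <10x, new wall motion abnormality | MI | MI | no |
| CK-MB 5x to <10x, new Q waves | MI | MI | MI |
| CK-MB 10x or more, no supporting finding | no | MI | MI |

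The three readings agree only in the first and fourth rows. The literal reading adds events in the second row and loses them in the fifth. If the event falls within 72 h of a PCI, the 5x/10x rule applies instead, so the same operation is judged differently according to when the PCI took place.

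**3. Which endpoints are reached**

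- *Primary PoCE.* Unplanned revascularization for ischemia is a component, and section 7.10 allows repeat CABG only with evidence of ischemia. The operation precedes any MI that it causes, so the patient's first event is normally already counted.
- *All MI and the periprocedural/spontaneous split.* Directly affected.
- *Target-vessel MI.* This is the default class: an MI is target-vessel unless clearly assigned elsewhere. The left main and its branches are target vessels, which leaves an untreated right coronary artery as the usual exception.
- *TVF and DoCE.* Clinically indicated revascularization ordinarily requires target-lesion stenosis of at least 50% by QCA plus an ischemia criterion. A CABG that meets this is already counted. A CABG for disease elsewhere, with a patent left main stent, may not meet it, yet could enter through target-vessel MI.

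**4. Size**

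The change in a crude rate from k misclassified patients is k/260. For k = 1, 1/260 = 0.38 percentage points; for k = 3, 3/260 = 1.15 points. The documents give no CABG rate, so k is unknown.

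**The case against.** The strongest reply is that the pointer is merely mislabelled. The SCAI block directly follows type 5, names CABG and has the same 48-hour window. A committee that follows the pointer down the page would reach a rule with high thresholds. Type 4a, nearby, refers to EXCEL and SCAI jointly. This may well be what was meant, but the documents do not settle it: type 5 names EXCEL only, and the two rules differ in window and in supporting criteria. If SCAI was intended, the text still needs correcting.

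It can also be said that type 5 sits in an optional table and that the CEC charter, which is not among the documents, may fill the gap. Both are fair. However, the operative EXCEL block has the same gap, and the charter has to work from the protocol's definitions.

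Three stronger readings are tempting and are not supported:

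- A reader might infer that any routine biomarker rise after CABG becomes a spontaneous MI. It does not: a supporting finding is required, and the ECG criterion excludes ST changes with other causes.
- A reader might infer that the primary comparison is biased. The CABG normally counts already.
- A reader might assume a CABG rate of 1% to 3% (260 x 0.01 = 2.6 to 260 x 0.03 = 7.8 patients) and conclude that the MI rate rises by 1 to 3 points. That rate has no source in the documents, and patients who may need surgery within a year are excluded. The sum also scores every CABG as an MI and ignores CABG within 72 hours of PCI. It is at best an upper bound on an assumption.

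**Conclusion.** The fault stands as a gap and a conflict in the endpoint definitions. The EXCEL-based definition has no class for MI after CABG, its spontaneous class does not exclude the peri-CABG period, and the type 5 entry refers to EXCEL text that does not exist where it points. A post-CABG event can be classed differently depending on which text the committee follows.

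The consequence is limited to secondary endpoints: all MI, the periprocedural/spontaneous split, target-vessel MI, and TVF and DoCE for CABGs that are not clinically indicated TVR or TLR. Each misclassified patient moves a crude rate by about 0.4 points. The number is probably small, given the surgical exclusion, but cannot be derived from the documents. The conclusion assumes that adjudication follows the protocol text as written and that a CABG during follow-up is normally unplanned and ischemia-driven. It is worth correcting, but it does not threaten the primary conclusion.

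**What to change.** Reconcile the MI entries in Appendix I:

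1. State in the operative MI definition which criteria apply after CABG, with one window. The 72 h and 48 h windows now conflict, and the type 5 heading must be brought into line. Name graft as well as native occlusion among the supporting criteria: the peri-procedural list has native occlusion only, so merely adding CABG to the two timing phrases would leave early graft occlusion supporting neither class.
2. Exclude that window after CABG, as well as after PCI, from spontaneous MI.
3. Point the type 5 entry to that text, or to SCAI if that was meant.
4. Align the CEC charter.

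Section 3 says that the endpoint definitions are meant to be similar to EXCEL, so the sponsor should check the CABG criteria against that source; the documents do not show what EXCEL used. The cost is a few words in Appendix I and a charter update, with no change to data collection, sample size or the primary analysis.
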